ANNEX 1 – IAQ MONITORING DEVICE

CONTINUOUS IAQ MONITORING: MICA-INBIOT

-	
inBio	·)
-	
	(inflic

Indoor temperatureUniversal communicationRelative HumidityHigh connectivityFormaldehydeCloud Platform VisualizationTVOCBMS IntegrationPM1/PM2.5/PM4/PM10HVAC ControlExternal weatherBI Data AnalysisCO2Data security	IAQ Parameters	Features
Relative HumidityHigh connectivityFormaldehydeCloud Platform VisualizationTVOCBMS IntegrationPM1/PM2.5/PM4/PM10HVAC ControlExternal weatherBI Data AnalysisCO2Data security	Indoor temperature	Universal communication
FormaldehydeCloud Platform VisualizationTVOCBMS IntegrationPM1/PM2.5/PM4/PM10HVAC ControlExternal weatherBI Data AnalysisCO2Data security	Relative Humidity	High connectivity
TVOC BMS Integration PM1/PM2.5/PM4/PM10 HVAC Control External weather BI Data Analysis CO2 Data security	Formaldehyde	Cloud Platform Visualization
PM1/PM2.5/PM4/PM10 HVAC Control External weather BI Data Analysis CO2 Data security	TVOC	BMS Integration
External weather BI Data Analysis CO2 Data security	PM1/PM2.5/PM4/PM10	HVAC Control
CO2 Data security	External weather	BI Data Analysis
	CO2	Data security
Modular design for self-installation and maintenanc		Modular design for self-installation and maintenance

	MICA - inBiot			
Particulate Matter	Removable laser-based light scattering sensor			
Particle Size	µg/m ³	0.3 - 10		
Measuring Range: PM2.5/PM10	µg/m ³	0-5000		
Sensor Output Resolution	µg/m ³	1.00		
Accuracy	%	0-35 µg/m3 - ±5 µg/m3 35 - 500 µg/m3 - ±15% reading		
тиос	Re	emovable MEMS metal oxide sensor		
Measuring Range	ppb	0-6000		
Sensor Output Resolution	ppb	0.2% reading		
Accuracy Baseline Correction	%	±15 Automatic		
Carbon Dioxide (CO2)		Non dispersive infrared sensor		
Measuring Range	ppm	0-5000		
Sensor Output Resolution	ppm	1		
Accuracy Baseline Correction	20	±(30+3%) ppm Automatic/based on ventilation system		
Temperature				
Measuring Range	°C	-0-90		
Sensor Output Resolution	°C	0.01		
Accuracy	°C	±0.2 - ±0.1		
Relative Humidity				
Measuring Range	%RH	0-100		
Sensor Output Resolution	%RH	0.01		
Accuracy	%	±2		
Formaldehyde		electromechanical sensor		
Measuring Range		0-6250		
Sensor Output Resolution		-		
Accuracy		<200 µg/m3: ±30 µg/m3 >200 µg/m3: ±20% measured		

ANNEX 2- HEALTH QUESTIONNAIRES

PART A. SOCIO-DEMOGRAPHIC DATA

Patient	ID:		
1.	In what year were you born?//		
2.	Please indicate your sex at birth:		
	1= Male	2= Female	3= Other
3.	Please indicate your highest level of schooling: 0= None 1= Early. Childhood education 2= Primary education 3= Lower Secondary education 4= Upper Secondary education		5= Short cycle Tertiary education 6= Bachelor's or equivalent level 7= Master's or equivalent level 8= Doctoral or equivalent level
4.	Please indicate your current relationship status: 0= Not married/partnered 1= Married/partnered 2= Divorced/separated		3= Widowed 4= Unknown
5.	What is your work status? 0= Unemployed 1= Part-time employment 2= Full-time employment	3= F 4= L hon	Retired Jnpaid work (student, caregiver, nemaker, volunteer, etc.)
6.	Living arrangements: 0=Lives alone 1=Lives with others		

2=Lives in supported home (i.e. assisted living, congregate care, skilled nursing home, etc.) 3=Homeless

PART B. THE ICHOM DATA SET FOR ADULT POPULATION

CLINICAL FACTORS

- 1. Have you ever been told by a doctor that you have any of the following?
 - 0= I have no other diseases
 - 1= Heart disease (angina, heart attack, heart failure)
 - 2= High Blood Pressure
 - 3= Lung Disease (asthma, chronic bronchitis, emphysema)
 - 4= Diabetes
 - 5= Stomach disease or ulcer
 - 6= Kidney disease
 - 7= Liver disease
 - 8= Blood disease or anemia
 - 9= Cancer

10= Depression 11= Osteoarthritis 12= Back pain 13= Rheumatoid Arthritis 14= Other medical problems: _____

If some of the other previous questions is YES: Do you receive treatment for (the related diseases answered yes)? 0=No 1=Yes Des your (the related diseases answered yes) limit your activities? 0=No 1=Yes

- 2. Systolic Blood Pressure: _____mmHG
- 3. Diastolic Blood Pressure: _____mmHG
- 4. Body mass index (kg/m2) : _____ (or ask for height and weight)
- 5. What is the patient's total cholesterol?
- 6. What is the patient's HDL cholesterol?
- 7. What is the patient's diabetes status?
 - 0=The patient is not diagnoses with diabetes
 - 1= The patient is diagnoses with Type I diabetes
 - 2= The patient is diagnoses with Type II diabetes

LIFESTYLE FACTORS

- 8. Please indicate your smoking behavior? More detailed definitions are as follows: Daily smoker: A person who smokes daily. Weekly smoker: A person who smokes at least weekly but not daily. Former smoker: A person who does not smoke at all now but has smoke.
 - 0= Daily smoker 1= Weekly smoker 2= Former smoker

3= Never-smoker 4= Others 999=unknown if ever smoked

- 9. How many standard alcoholic drinks do you drink per week? One standard drink is equal to 12.5ml of pure alcohol, or roughly 1 small glass of wine/25cl of regular beer (5% alcohol).
- 10. Physical activity.
 - *a.* On average, how many days per week do you engage in moderate to strenuous exercise (like a brisk walk, slow biking, general gardening)?_____
 - b. On average, how many minutes, per day, do you engage in exercise at this level?_____
 - c. On average, how many minutes, per day, do you engage in exercise at this level?_____
 - d. Total minutes per week of physical activity (multiply PAVSDAY by PAVSTIME)

0= 0 minutes

1= 1-150 minutes

2= >150 minutes

SEEING

11. At the present time, would you say your eyesight, with glasses or contact lenses if you wear them is...

- 5= excellent
- 4= very good
- 3=good

HEARING

2= fair

12.	Would you say your hearing is				
	5= excellent	2= moderate	hearing	0=deaf	
	4= good	trouble			
	3=a little trouble	1= a lot of troub	le		
OUTCO	MES				
13.	In general, would you say your health is:				
	5 = Excellent		2 = Fair		
	4 = Very good		1 = Poor		
	3 = Good				
	5 - 0000				
1/	In general, would you say your quality of	ifo is:			
14.	5 - Excellent	iie 13.	2 - Fair		
			1 = POOT		
	3 = Good				
15.	In general, how would you rate your phys	ical health?			
	5 = Excellent		2 = Fair		
	4 = Very good		1 = Poor		
	3 = Good				
16.	In the past 7 days, how would you rate yo	our fatigue on ave	rage?		
	5 = None		2 = Severe		
	4 = Mild		1 = Very severe		
	3 = Moderate				
17.	In the past 7 days, how would you rate yo	our pain on average	ge?		
	0 1 2 3 4	5 6	7 8 9	10	
18.	To what extent are you able to carry ou	t your everyday	physical activities such	as walking, climbing stairs,	
	carrying groceries, or moving a chair?			.	
	5 = Completely		2 = A little		
	4 = Mostly		1 = Not al all		
	3 = Moderately				
	,				
19	In general, how would you rate your men	tal health includi	ng your mood and your	ability to think?	
15.	5 = Excellent				
	4 = Very good		1 - Poor		
	2 = Cood		1 - FOOI		
	3 - 8000				
20	to the west 7 days have after have see		h	a such as fasting and a	
20.	In the past 7 days, now often have you	u been bothered	by emotional problem	is such as reeling anxious,	
			2 Often		
	5 = Never		2 = Often		
	4 = Rarely		1 = Always		
	3 = Sometimes				
		•			
21.	In general, how would you rate your satis	taction with your	social activities and rela	tionships?	
	5 = Excellent		2 = Fair		
	4 = Very good		1 = Poor		
	3 = Good				

22. In general rate how well you carry out your usual social activities at home, at work and in your community, and responsibilities as a parent, child, spouse, employee, friend, etc.)?
5 = Excellent
4 = Very good

K-HEALTH

nAIR

	30/11/2023 v.10	K-HEALTHinAIR - Knowledge for improving indoor AIR quality and HEALTH			
	3 = Good 2 = Fair	1 = Poor			
23.	In the past 30 days, how much dif 0 = None 1 = Mild 2 = Moderate	ficulty did you have in standing for long periods such as 30 minutes? 3 = Severe 4 = Extreme or cannot do			
24.	In the past 30 days, how much dif 0 = None 1 = Mild 2 = Moderate	ficulty was taking care of your household responsibilities? 3 = Severe 4 = Extreme or cannot do			
25.	In the past 30 days, how much diplace? 0 = None 1 = Mild 2 = Moderate	fficulty was learning a new task, for example, learning how to get to a new 3 = Severe 4 = Extreme or cannot do			
26.	In the past 30 days, how much festivities, religious or other activi 0 = None 1 = Mild 2 = Moderate	of a problem did you have joining in community activities (for example, ties) in the same way as anyone else can? 3 = Severe 4 = Extreme or cannot do			
27.	In the past 30 days, how much hav 0 = None 1 = Mild 2 = Moderate	ve you been emotionally affected by your health problems? 3 = Severe 4 = Extreme or cannot do			
28.	In the past 30 days, how much diff 0 = None 1 = Mild 2 = Moderate	ficulty was concentrating on doing something for ten minutes? 3 = Severe 4 = Extreme or cannot do			
29.	In the past 30 days, how much diff 0 = None 1 = Mild 2 = Moderate	ficulty was walking a long distance such as a kilometer [or equivalent]? 3 = Severe 4 = Extreme or cannot do			
30.	In the past 30 days, how much diff 0 = None 1 = Mild 2 = Moderate	ficulty was washing your whole body? 3 = Severe 4 = Extreme or cannot do			
31.	In the past 30 days, how much dif 0 = None 1 = Mild 2 = Moderate	ficulty was getting dressed? 3 = Severe 4 = Extreme or cannot do			
32.	In the past 30 days, how much dif 0 = None 1 = Mild	ficulty was dealing with people you do not know? 4 = Extreme or cannot do			

3 = Severe

- 33. In the past 30 days, how much difficulty was maintaining a friendship?
 - 0 = None
 - 1 = Mild
 - 2 = Moderate
 - 3 = Severe
 - 4 = Extreme or cannot do

34. In the past 30 days, how much difficulty was your day-to-day work?

- 0 = None
- 1 = Mild
- 2 = Moderate
- 3 = Severe
- 4 = Extreme or cannot do
- 35. Over the past 2 weeks: 1. I have felt cheerful and in good spirits
 - 5= All of the time
 - 4= Most of the time
 - 3= More than half the time
 - 2= Less than half the time
 - 1= Some of the time
 - 0= At no time

36. Over the past 2 weeks: 2. I have felt calm and relaxed

- 5= All of the time
- 4= Most of the time
- 3= More than half the time
- 2= Less than half the time
- 1= Some of the time
- 0= At no time
- 37. Over the past 2 weeks: 3. I have felt active and vigorous
 - 5= All of the time
 - 4= Most of the time
 - 3= More than half the time
 - 2= Less than half the time
 - 1= Some of the time
 - 0= At no time
- 38. Over the past 2 weeks: 4. I woke up feeling fresh and rested
 - 5= All of the time
 - 4= Most of the time
 - 3= More than half the time
 - 2= Less than half the time
 - 1= Some of the time 0= At no time
- 39. Over the past 2 weeks: 5. my daily life has been filled with things that interest me 5= All of the time
 - 4= Most of the time
 - 3= More than half the time
 - 2= Less than half the time
 - 1= Some of the time
 - 0= At no time

PART C ADAPTATION OF THE PARIS SURVEY

ACCESIBILITY

- 1. How easy or difficult is it to get medical care in the evenings, on weekends, or holidays without going to the hospital?
 - 1= Very easy
 2= Somewhat easy
 3= Somewhat difficult
 4= Very difficult
 6 (DO NOT READ) Never needed care in the evenings, weekends, or holidays
 D (DO NOT READ) Not sure
 R (DO NOT READ) Decline to answer
- 2. How quickly did you get an appointment to see your doctor?
 - 1= Very quickly
 - 2= Somewhat quickly
 3= Somewhat difficult
 4= Very difficult
 6 (DO NOT READ) Never needed care in the evenings, weekends, or holidays
 D (DO NOT READ) Not sure
 R (DO NOT READ) Decline to answer
- 3. Was the time you waited for the appointment for your doctor? (in days)
 - ___ [RANGE 0-96]
 - 1 (DO NOT READ) More than one doctor but doesn't know exact number D (DO NOT READ) Not sure
 - R (DO NOT READ) Decline to answer
- 4. On the actual day of the consultation, how long did you wait (for example in the doctor's waiting room) before you were actually seen? (in minutes)

[RANGE 0-96] 1 (DO NOT READ) More than one doctor but doesn't know exact number D (DO NOT READ) Not sure R (DO NOT READ) Decline to answer

- 5. Was the time you waited to be seen a problem for you?
 - 1 =Yes

2 =No D (DO NOT READ) Not sure R (DO NOT READ) Decline to answer

COMMUNICATION

6. Did the doctor/nurse spend enough time with you?

1 =Yes

2 =No D (DO NOT READ) Not sure R (DO NOT READ) Decline to answer

7. During your communication with the health staff, how often did your doctor/nurse treat you with courtesy and respect?

1 =Always

- 2 =Often
- 3 =Sometimes
- 4 =Rarely or never
- 5 =(DO NOT READ) Never tried to contact by telephone
- D (DO NOT READ) Not sure

R (DO NOT READ) Decline to answer

8. Did this give you an opportunity to ask questions or raise concerns about recommended treatment?

1 =Yes

2 =No D (DO NOT READ) Not sure R (DO NOT READ) Decline to answer

SHARED DECISION MAKING

 During the past year, when you received care, has any health care professional you see for your [insert condition] discussed with you your main goals or priorities in caring for this condition 1 =Yes

> 2 =No D (DO NOT READ) Not sure R (DO NOT READ) Decline to answer

 Did this involve you as much as you wanted to be in decisions about your care and treatment? 1 =Yes

2 =No D (DO NOT READ) Not sure R (DO NOT READ) Decline to answer

CONTINUITY AND COORDINATION

- 11. Is there one doctor you usually go to for your medical care?
 - 1 =Yes, have a regular doctor/GP

2 =(DO NOT READ) Yes, but have more than one regular doctor/GP 3 =No 4 =Yes, have nurse practitioner or physician assistant D (DO NOT READ) Not sure R (DO NOT READ) Decline to answer

12. Not counting any time you may have been hospitalized, how many different doctors have you seen in the past 12 months?

[RANGE 0-96] 1 (DO NOT READ) More than one doctor but doesn't know exact number D (DO NOT READ) Not sure R (DO NOT READ) Decline to answer

13. Now thinking about the past 2 years, when receiving care for a medical problem, was there EVER a time when doctors ordered a medical test that you felt was unnecessary because the test had already been done?

1 =Yes, this happened 2 =No 3 =(DO NOT READ) Not Applicable D (DO NOT READ) Not Sure R (DO NOT READ) Decline to Answer

14. In the past 12 months, has a doctor or pharmacist reviewed with you all the medications you take?

1 Yes

2 No D (DO NOT READ) Not sure R (DO NOT READ) Decline to answer

PART D. QUALITY OF LIFE (EQ-5D-5L)

Under each heading, please tick the ONE box that best describes your health TODAY.

MOBILITY			
I have no problems in walking about		Υ	
I have slight problems in walking about	Υ		
I have moderate problems in walking about	·Ύ		
I have severe problems in walking about	Ϋ́		
Lam unable to walk about	Υ		
	1		
SELE-CARE			
Lhave no problems washing or dressing my	colf		r
L have slight problems washing of dressing my	mucolf		Ι Υ
I have slight problems washing of dressing i	ing muc	.it	l Y
I have moderate problems washing or dress	sing myse	:11	l Y
I have severe problems washing or dressing	mysen		1
I am unable to wash or dress myself			1
	work fo	milu ou la	
USUAL ACTIVITIES (e.g. work, study, nouse	work, ta	\sim	sure activities)
I have no problems doing my usual activities	S	1	
I have slight problems doing my usual activi	ties	I	
I have moderate problems doing my usual a	activities	Y	
I have severe problems doing my usual activ	vities	Ŷ	
I am unable to do my usual activities			Ŷ
PAIN / DISCOMFORT	24		
I have no pain or discomfort	1		
I have slight pain or discomfort	Y		
I have moderate pain or discomfort Υ			
I have severe pain or discomfort Υ			
I have extreme pain or discomfort Υ			
ANXIETY / DEPRESSION			
I am not anxious or depressed		Υ	
I am slightly anxious or depressed	Υ		
I am moderately anxious or depressed		Ŷ	
I am severely anxious or depressed	Ŷ		
I am extremely anxious or depressed		Υ	

•

We would like to know how good or bad your health is TODAY. The best health This scale is numbered from 0 to 100. \rightarrow 100 means the best health you can imagine 100 you can imagine / 0 means the worst health you can imagine.
 III
 III</t 95 Please mark an X on the scale to indicate how your health is TODAY. 90 Now, write the number you marked on the scale in the box below. 85 80 75 70 65 55 50 45 40 YOUR HEALTH TODAY = 35 30 25 20 15 10 5

The health you can imagine

0

PART E. MENTAL HEALTH (PHQ-9)

ID:_____

DATE:_____

Over the last 2 weeks, how ofter have you been bothered by any of the following problems?

		NOT	SEVERAL	MORE	NEARLY
		AT	DAYS	THAN	EVERY
		ALL		HALF	DAY
				DAYS	
1.	Little interest or pleasure in doing things.	0	1	2	3
2.	Feeling down, depressed, or hopeless.	0	1	2	3
3.	Trouble falling or staying asleep or sleeping too much.	0	1	2	3
4.	Feeling tired or having little energy.	0	1	2	3
5.	Poor appetite or overeating.	0	1	2	3
6.	Feeling bad about yourself-or that you are a failure or have let yourself or your family down.	0	1	2	3
7.	Trouble concentrating on things, such as reading the newspaper or watching television.	0	1	2	3
8.	Moving or speaking so slowly that other people could have noticed. Or the opposite – being so figety or restless that you have been moving around a lot more than usual	0	1	2	3
9.	Thoughts that you would be better off dead, or of hurting yourself.	0	1	2	3
		++			
		тот	AL:		_
10.	If you checked off any problems, how difficult have these problems made it for you to do your work, take care of things at home, or get along with other people?	 Not difficult at all Somewhat difficult Very difficult Extremely difficult

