1.3.3.2 Patients' health status and use of healthcare resources

The clinical information of the patients enrolled in the study will be obtained from different sources:

C) Electronic Health Records, from the Hospital Clinic of Barcelona (SAP) and primary care (eCAP) will be used as a source of information on clinical episodes and procedures.

TABLE 3 – Health information retrieved from hospital and primary care health records.

Feature	Units
Disease diagnosis	ICD10
Clinical procedures	ICD10
Hospital admissions - Length of stay	date - days
ICU length of stay (if applicable)	days
Lab tests	miscellaneous
Visits (outpatients, ER, day hospital, etc)	Episode date, type
Frailty (functional, social, etc)	Standardized records

D) **Standardized questionnaires** will be utilized to assess general and mental health, quality of life and patient's experience. The questionnaires will be dispensed at study entry and periodically administered throughout the study period (for detailed information on the questionnaires see Annex 2).

TABLE 4 – General health, mental health, quality of life and patient reported experience questionaries administered.

Feature	Units	Periodicity
General Health Questionnaires	ICHOM Adult Set	Every 6 months
Mental Health Questionnaires	PHQ-9	Every 2 months
Quality of Life Questionnaires	EQ-5D-5L	Every 2 months
Patient Reported Experience	PARIS (adapted)	Every 6 months

E) Registry data will be yearly extracted from the Catalan Health Surveillance System (CHSS), encompassing:

TABLE 5 – Hea	Ith information	retrieved from	health registries.
---------------	-----------------	----------------	--------------------

Feature	Units
Disease diagnosis	ICD10
Medication prescribed	ATC
Utilization of healthcare resources	Number of encounters with healthcare professionals at
	different levels; primary care visits, outpatient care visits,
	mental health ambulatory visits, emergency room visits,
	day hospital visits, intermediate care admissions, hospital
	admissions, admissions in mental health centers.
Total healthcare expenditure	€

F) Assessment of pulmonary capacity through FOT and FS measurements that will be performed at entry into the study and every 6 months. Measurements will be done using Lothar-Medtech equipment (https://alds.health/).

Feature	Units	Periodicity
FS (FVC, FEV1, FEV1/FVC ratio)	(ml, ml, %)	Every 6 months
FOT resistance (R5 and R5-20)	Pressure/meter/second	Every 6 months
FOT reactance (X)	Pressure/volume	Every 6 months

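### Five of the 14 items in the adapted PARIS survey carry a coding or response-option error, and three of them (items 2, 4 and 12) can distort the recorded answers

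*Protocol*

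**What the plan says.** Section 1.3.3.2 (Table 4) names the adapted PARIS survey as the patient-reported experience questionnaire, given every 6 months. Annex 2, Part C prints the form.

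- **Item 12** asks "how many different doctors have you seen in the past 12 months", takes a number from 0 to 96, and lists "1 (DO NOT READ) More than one doctor but doesn't know exact number" among the answers that the interviewer does not read out.
- **Item 3** (days waited for an appointment) and **item 4** (waiting time on the day, "before you were actually seen? (in minutes") have the same 0 to 96 range and the same special answer under code 1, again beginning "1 (DO NOT READ) More than one doctor but".
- **Item 2** asks "How quickly did you get an appointment to see your doctor". Codes 1 and 2 are degrees of quickness, and codes 3 and 4 are degrees of difficulty. Skip code 6 is for patients who never needed care outside normal hours. Codes 3, 4 and 6 repeat item 1.
- **Item 7** asks how often staff were courteous and respectful. It includes the unread option "DO NOT READ) Never tried to contact by telephone".

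No other part of the protocol corrects these codes or gives a different coding for the survey.

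**The concern.** A special answer needs a code that cannot also be a real answer. In item 12 the special answer means more than one doctor, while the code it is given is the valid count for exactly one. If both go into one field, two opposite answers share a value, and no later analysis can separate them from that field alone.

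The other faults look like options carried over from neighbouring questions. They matter where they limit or change what a patient can answer: a long wait in item 4, or a slow appointment in item 2.

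What is at stake is the patient-experience measure. Item 12 sits under continuity and coordination. Section 1.3.1.1 gives the nurse case manager the tasks of ensuring continuity of care and linking primary and specialised care, so the item concerns something the programme is meant to influence.

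**Working it through.** The protocol gives no figure to reproduce here. The check is a count of items and a comparison of each question with its printed answers.

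**Number of items.** Accessibility 1–5, communication 6–8, shared decision making 9–10, continuity and coordination 11–14: 5 + 3 + 2 + 4 = 14. The last is "14. In the past 12 months, has a doctor or pharmacist reviewed with you all the medications you take".

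| Item | Asks for | Fault as printed | Effect |
|---|---|---|---|
| 2 | Speed of getting an appointment | Codes 3 and 4 are about difficulty; code 6 is about out-of-hours care | The meaning of the scale changes half-way; the skip code does not match |
| 3 | Days waited | Special answer about doctors under code 1, inside 0–96 | Option makes no sense here and would seldom be used |
| 4 | Minutes waited | Same special answer; range ends at 96 | Waits above 96 minutes (1 h 36 min) cannot be entered |
| 7 | Courtesy and respect | Code 5 is about telephone contact | Codes 1–4 fit and can be scored |
| 12 | Number of doctors | Special answer under code 1, inside 0–96 | A 1 can mean one doctor or several |

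**Counts.**
- Special code inside the valid range: items 3, 4, 12 = 3/14 = 21%.
- Options that do not belong to the question: items 2, 3, 4, 7 = 4/14 = 29%.
- Any of these faults: items 2, 3, 4, 7, 12 = 5/14 = 36%; without item 7, 4/14 = 29%.
- Able to distort recorded data: items 2, 4, 12 = 3/14 = 21%. This is a different set of three from the first line.
- Shared code that joins two plausible but opposite answers: item 12 only = 1/14 = 7%, and only at the value 1.

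**Illustration for item 12, on assumed inputs.** Suppose the special answer shares the count field. Let q be the share of patients giving it and M their true mean number of doctors. Recording them as 1 lowers the mean by q × (M − 1). The protocol gives neither q nor M.
- Assume q = 5%, 10%, 20%, with M and the overall mean both 4. The recorded mean is 4 − 3q = 3.85, 3.70, 3.40, which is 4% to 15% too low.
- With M = 2, the lowest value that more than one doctor allows, the drop is only q × 1 = 0.05 to 0.20.
- With the planned 200 patients, q of 5% to 20% is 10 to 40 patients per wave.

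These figures show how the error would work. They do not estimate its size.

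**The case against.** The strongest reply is that the printed form is not the database. Section 1.3.3 says that these data are held in REDCap, whose field definitions are not shown. The same answer list has letter codes (D and R), which a purely numeric field cannot take. The build therefore needs either a text field or a separate variable for special answers, and with a separate variable item 12 has no collision. This stands. It makes the collision conditional on the form having been entered as printed.

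A second reply is that a character before the 1 may have been lost when the PDF was read. That cannot be fully excluded, but the same 1 appears in three items, and the misplaced options are whole phrases that no lost character explains.

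A reader might infer that a third of the survey cannot be scored. The documents do not support that. Item 7 works if code 5 is treated as not applicable. A 1 in item 3 or 4 is almost surely one day or one minute. Item 2's four options still run from better to worse, although their meaning is mixed.

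A reader might also infer that the error is beyond repair, or that it flatters continuity of care. The first depends on the unseen build. For the second, the recorded count could only be pulled down, but the protocol gives no scoring rule that makes one doctor the best answer.

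Finally, no objective, analysis group or expected outcome (sections 1.2, 1.3.3.4, 1.5) names a PARIS score, and section 1.4.1.2 mentions further experience measures collected through the App. This stands too and limits the weight of the point.

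**Conclusion.** The point holds as a fault in a data-collection form. Five of 14 items carry a coding or response-option error. Used as printed, three can give ambiguous, truncated or mixed answers: item 12 (one doctor against several), item 4 (waits above 96 minutes) and item 2 (speed against difficulty). Items 3 and 7, and item 4 apart from its upper limit, remain largely scorable.

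The item 12 conclusion assumes that the special answer was entered as code 1 in the same field as the count. How many patients are affected, and by how much, cannot be learned from the protocol. The effect is confined to the 6-monthly patient-experience measure. The core analysis of indoor air quality and acute events does not use these items.

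**What to change.** In Annex 2, Part C and the matching REDCap and App fields:

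- **Item 12:** give the special answer a code outside 0–96, or a letter code like D and R.
- **Items 3 and 4:** delete that answer.
- **Item 4:** widen the range so that long waits can be entered.
- **Item 2:** use a single speed scale, with a skip code for patients who did not seek an appointment.
- **Item 7:** remove the telephone code.

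For data already collected, first look at the REDCap field coding. Flag values of 1 as ambiguous in item 12 only, and only if the special answer shared that field. Flagging every 1 in items 3 and 4 would discard valid answers.

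The cost is a form edit and a version marker in the data, because item 2 before and after the change will not be directly comparable. The annex is dated 30/11/2023 and follow-up runs to March 2026 (section 1.3.2). If recruitment finished in July–August 2023 as planned, 6-monthly waves from early 2024 to early 2026 (months 6, 12, 18, 24 and 30) still lay ahead of that version.
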